To compare the effect of chewing gum and honey on postoperative recovery and complications in ileostomy reversal (as mentioned below).

OPERATIONAL DEFINITIONS

1. **Early enteral nutrition:** Defined as oral intake started on the first postoperative day. In contrast, the traditional way of normal enteral nutrition is nothing by mouth until the resolution of ileus, then a fluid diet, followed by a regular diet (27).

2. **Ileostomy reversal:** When the ileum previously used to form the stoma i.e. Loop Ileostomy, Double Barrel Ileostomy, Ileocolostomy or End Ileostomy is reconnected to the remainder of the bowel internally (31).

3. **Postoperative recovery and complications:**

- **Time to bowel sounds:** Defined as the time, in hours, between the completion of surgical closure and the first audible auscultation of non-continuous, high-pitched bowel sounds originating from the reconnected intestine, documented by a trained healthcare professional using a stethoscope placed over the lower quadrants of the abdomen (32,33).
- **Time to pass flatus:** Defined as the time, in hours, between the completion of surgery and the documented passage of the first objectively confirmed flatus by auscultation or direct observation (33).
- **Time to pass feces:** Defined as the time, in hours, between the completion of surgery and the documented first independent bowel movement, excluding any stool manually evacuated or stimulated by laxatives (33).
- **Time to full feeds:** Defined as the time, in hours, between the surgery and the first point at which the patient tolerates and consumes a regular, unrestricted diet without experiencing any significant postoperative gastrointestinal complications (e.g., nausea, vomiting, abdominal pain, ileus) for a predetermined timeframe (i.e., 24 hours) (7,26).
- **Postoperative pain:** Postoperative pain in stoma reversal surgery was defined as the subjective pain intensity experienced by the patient at rest or during movement, assessed using the Visual Analog Scale (VAS). The VAS consists of a 10 cm horizontal line anchored by "no pain" (score of 0) and "worst imaginable pain" (score of 10), with patients marking the point on the line that best represented their pain intensity (4).

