- **Postoperative ileus:** Postoperative ileus is an abnormal pattern of slow or absent gastrointestinal motility in response to surgical procedures. It is measured as the absence of flatus/stool and inability to tolerate an oral diet within 3 days after surgery (34) (35).
- **Postoperative nausea and vomiting (PONV):** PONV is defined as documented postoperative nausea/emesis or administration of a rescue antiemetic (36).
- **Length of postoperative stay:** Defined as the time, in hours, from completion of reversal surgery to the time of discharge from the hospital (14).

HYPOTHESIS

There is a significant difference in the effect of chewing gum and honey on postoperative recovery and complications in ileostomy reversal.

MATERIALS AND METHODS

METHODS

Trial Design: Prospective single-blinded randomized controlled trial. Parallel design with allocation ratio 1:1 will be used. This manuscript is a protocol for the pilot RCT.

Participants: Patients presenting to the outdoor and ward of West Surgical Department with an Ileostomy and undergoing Ileostomy reversal surgery in the operation theatre.

Study Setting and Location: Male and Female Ward, West Surgical Department, Mayo Hospital, Lahore

Sample Size:

Due to deficiency of literature about the use of honey in gastrointestinal surgery and specifically intestinal anastomosis, it was decided that pretesting with a pilot study would be conducted to calculate the sample size. The overall sample size of 30 participants for the pilot trial was selected according to the Rule of Thumb for pilot trial sample size calculation. 15 participants in each group, i.e. Group A for chewing gum and Group B for honey, were allocated randomly using the lottery method. The primary outcome variable was time to pass flatus. The results of the pilot trial for the primary outcome variable showed that the mean time to pass flatus in Group A was 67.73 ± 8.481 hours and Group B was 75.73 ± 9.968 hours.

Outcome Variable	Group A		Group B		Population SD (σ)	Sample Size (n)
	Mean	SD	Mean	SD		
Bowel sounds	51.20	9.937	59.20	8.970	9.466	31
Time to pass flatus	67.73	8.481	75.73	9.968	9.254	29
Time to pass stools	100.80	11.632	119.47	12.994	12.332	10
Time for full feeds	79.47	10.239	93.33	11.178	10.719	13

The means and standard deviations of the pilot trial data was used to calculate the sample size using WHO Sample Size Calculator using the formula for hypothesis tests for two population means (one-sided test) as follows:

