Allocation: Patients will be randomly allocated in group A or B: A for the Oral Chewing Gum group and B for the Oral Honey group using the lottery method by the principal investigator.

Sequence Generation: The lottery method is a simple form of simple randomization used to assign participants into the two groups in a way that ensures unbiased allocation. Each participant will be assigned a case number from 1 onwards based on their induction into the study by the principal investigator. 30 identical paper slips will be made and Group A will be written in 15 slips and Group B will be written on the other 15 slips. The slips will be folded to conceal the written text. The slips will be mixed thoroughly and drawn randomly, and the participants will be assigned to a group based on the identifier on the slip, i.e. either Group A (chewing gum) or Group B (honey).

Concealment: The identifier “Group A” or “Group B” will be written on identical slips of paper and the slips will be folded to conceal the written text, ensuring blinding by making them indistinguishable.

Implementation:

The random allocation will be done by the principal investigator. The participants presenting to the out-patient clinic for ileostomy reversal will be admitted to the ward and enrolled into the study after fulfilling the inclusion criteria and passing the exclusion criteria by the principal investigator.

After a period of 24 hours from the ileostomy reversal surgery, the patients will be asked to start early water sips intake according to the ERAS protocol (6). Group A patients will be asked to chew gum for 5 minutes every 4 hours. Group B patients will be asked to eat one half tablespoon of natural honey every 4 hours. The outcome parameters will be assessed and

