Statistical analysis of the data will be carried out using IBM SPSS Statistics V26.0 for the Window program (IBM, Armonk, New York, USA). Qualitative variables such as gender, presence or absence of postoperative complications will be analyzed using frequencies and percentages. Quantitative variables such as age, length of postoperative stay, time to full feeds, time to bowel sounds, time to pass flatus and time to pass feces will be analyzed by calculating their mean and standard deviation. The data collected will be analyzed using descriptive statistics, such as frequencies, percentages, and means. Chi-Square test and logistic regression will be used to analyze the categorical variables whereas continuous variables will be analyzed using student t-test. Outcome data of the three groups will be compared to see the statistically significant difference, p-value of < 0.05 will be considered statistically significant. Outcome data will be stratified for age, gender, operative surgery, postoperative complications and post stratification chi square test will be applied. All qualitative data will be evaluated using

frequency tables. Any changes in the pre-operative and post-operative values will be calculated in absolute as well as percentages. The data will be explored using descriptive studies.

REFERENCES

2. de Gaay Fortman DPE, Kroon HM, Bedrikovetski S, Fitzsimmons TR, Dudi-Venkata NN, Sammour T. A snapshot of intraoperative conditions to predict prolonged postoperative ileus after colorectal surgery. *ANZ J Surg* [Internet]. 2022 Sep;92(9):2199–206. Available from: <http://www.ncbi.nlm.nih.gov/pubmed/35579059>

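### Outcomes are to be stratified by postoperative complications, which arise after randomisation and, for ileus, overlap time to flatus, so gum-versus-honey comparisons within those strata are distorted

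*Combined protocol and SAP*

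**What the plan says.** The Data Analysis Procedure plans this stratified analysis: "Outcome data will be stratified for age, gender, operative surgery, postoperative complications and post stratification chi square test will be applied". It does not call the analysis descriptive or exploratory. It does not say which complications form the strata or how a factor arising after randomisation would be handled.

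Other parts of the plan treat complications as outcomes:

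- The Hypothesis is that gum and honey differ in their effect on "postoperative recovery and complications".
- The Operational Definitions put recovery times, ileus and postoperative nausea and vomiting (PONV) under one heading. Ileus is measured as "absence of flatus/stool and inability to tolerate an oral diet within 3 days after surgery", and PONV as "documented postoperative nausea/emesis or administration of a rescue antiemetic". Time to flatus, the primary outcome, is counted from completion of surgery.
- The Exclusion Criteria remove patients who already have these complications, so a complication stratum can form only after entry.
- Under Implementation, gum or honey starts "After a period of 24 hours from the ileostomy reversal surgery".

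On tests, the same section assigns chi-square and logistic regression to categorical variables, "whereas continuous variables will be analyzed using student t-test". Chi-square is the only test named after stratification.

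**The concern.** A comparison within strata keeps the protection of randomisation only if treatment cannot affect who falls into each stratum. Age, gender and operative surgery meet that condition, because all three are fixed before gum or honey begins. Complications do not: the plan's own hypothesis is that treatment affects them.

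Ileus adds a second problem. Part of its definition is late flatus, so the uncomplicated stratum is partly selected for early flatus and the complicated stratum for late flatus, in both arms. Selecting on the outcome pulls the arm means together. A true difference could then be reported as smaller or absent within strata, and be read as contradicting the main result when the split itself caused the shrinkage.

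A smaller point is that most outcomes are times, while the only post-stratification test named is chi-square. The test for stratified times is therefore unclear.

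**Working it through.** **Inputs (Sample Size section).** Pilot time to flatus: gum 67.73 h (SD 8.481), honey 75.73 h (SD 9.968), difference 8.00 h; 30 patients per arm. The 72 h cut is the 3 days in the ileus definition. Normality is assumed.

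**The plan's own figure.** One-sided 5%, 95% power: n = 2 × 9.2245² × (1.645 + 1.645)² / 8.00² = 28.8, so 29 per arm, or 58 in total against the stated 60. The pilot values are therefore the planning values. (The multiplier 1.96 printed beside the formula is a separate matter.)

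**Step 1: who passes flatus after 72 h.** With a = (72 − mean)/SD:

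- Gum: a = (72 − 67.73)/8.481 = 0.503; P(late) = 1 − Φ(0.503) = 0.307.
- Honey: a = (72 − 75.73)/9.968 = −0.374; P(late) = 1 − Φ(−0.374) = 0.646.

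The cut lies between the two pilot means, so it selects the arms very differently.

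**Step 2: means on each side of the cut.** Late mean = mean + SD × φ(a)/P(late); early mean = mean − SD × φ(a)/(1 − P(late)).

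| | Early | Late |
|---|---|---|
| Gum | 63.43 | 77.43 |
| Honey | 65.26 | 81.47 |
| Difference (h) | 1.83 | 4.04 |

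**Step 3: only a fraction f of late patients count as complicated.** Ileus also needs diet intolerance, so f may be well below 1. If the fraction is drawn at random, the uncomplicated mean is [(1 − P) × early + (1 − f) × P × late] / (1 − fP). For f = 0.5:

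- Gum: (0.693 × 63.43 + 0.154 × 77.43)/0.846 = 65.97.
- Honey: (0.354 × 65.26 + 0.323 × 81.47)/0.677 = 72.99.
- Difference: 7.02 h.

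Pooling uses weights n1 × n2/(n1 + n2). For f = 1 the weights are 6.25 (complicated) and 7.03 (uncomplicated), giving (6.25 × 4.04 + 7.03 × 1.83)/13.28 = 2.87 h.

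| f | Complication rate, gum / honey | Uncomplicated (h) | Complicated (h) | Pooled (h) |
|---|---|---|---|---|
| 1 (limiting case) | 30.7% / 64.6% | 1.8 | 4.0 | 2.9 |
| 0.75 | 23.0% / 48.4% | 5.5 | 4.0 | 5.0 |
| 0.5 | 15.4% / 32.3% | 7.0 | 4.0 | 6.4 |
| 0.25 | 7.7% / 16.1% | 7.7 | 4.0 | 7.3 |

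**Step 4: the diet criterion modelled directly.** Take ileus as flatus after 72 h and full feeds after 72 h, with pilot feeds times 79.47 (SD 10.239) and 93.33 (SD 11.178) and an assumed correlation of 0 to 0.9. Ileus rates are then 0.24–0.31 (gum) and 0.63–0.65 (honey). The flatus difference is 3.9–4.0 h with ileus and 1.3–1.8 h without. Full feeds after 72 h is only a stand-in for diet intolerance.

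**Step 5: unrelated complications also count.** If events unrelated to flatus, such as PONV, occur in an assumed 20–40% of each arm, the uncomplicated differences do not change. The complicated-stratum difference becomes 6.8–8.1 h, and the pooled difference 4.8–7.9 h.

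**Step 6: power.** Simulated two-sided t-test, 30 per arm: 91% unstratified. For f = 1, 0.75, 0.5 and 0.25 it is 12%, 50%, 74% and 84% in the uncomplicated stratum, and 33%, 24%, 14% and 9% in the complicated stratum. The complicated figures count only runs with at least 2 patients per arm in the stratum (66% of runs at f = 0.25).

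**Step 7: chi-square on times.** If times were cut into two categories, uncorrected power over all 60 patients would be about 76% (72 h cut) to 80% (median split), against 91% for the t-test.

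**The case against.** The strongest reply is that the consequence is limited and its size unknown. The main t-test does not change, nor do the primary outcome and the sample size. The plan does not say which complications form the strata. With f at 0.25 to 0.5 the uncomplicated difference is 7.0–7.7 h against 8.0 h, and if PONV-type events also count, the pooled difference at those values of f is 7.2–7.9 h. If absence of stool alone met the ileus criterion, over 99% of both arms would meet that part at 72 h; ileus would then turn on diet intolerance and overlap less with flatus. All of this stands, and it is why the size is given as a range.

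Two technical objections also stand. First, the power figures mix bias with smaller strata. With an undistorted 8.0 h difference at about the expected uncomplicated stratum sizes, power would be 63%, 72–73%, 80–81% and 87% for f = 1, 0.75, 0.5 and 0.25. At f = 0.25, most of the fall from 91% is therefore lost sample size. The differences in hours are the measure of bias. Second, the constant 4.0 h assumes late patients are classed as complicated at random. If the chance rose linearly from 72 to 92 h, the differences would be 4.8 h (complicated) and 5.0 h (uncomplicated), still well short of 8.0 h.

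It can also be said that chi-square is the only test named, so a t-test on times within strata may not be intended. But the sentence covers outcome data without restriction, and the times are most of the outcomes. Finally, if treatment affected neither flatus nor complications there would be no bias, but the plan hypothesises an effect and sizes the trial on 8 h.

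None of this removes the fault. PONV does not overlap flatus by definition, yet it too is an outcome arising after randomisation.

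**Conclusion.** The concern holds. As written, the plan tests treatment differences within strata formed by an outcome, and for ileus that outcome is partly the primary endpoint. Under the pilot values and random classification of late patients, a true 8.0 h difference becomes 1.8 to 7.7 h among uncomplicated patients and 4.0 h among complicated patients. The complicated figure is 6.8–8.1 h if unrelated complications at 20–40% also count. The 1.8 h end is a limiting case. The direction of the problem is certain if treatment has the effect the plan assumes; its size is not.

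This should be fixed before analysis, but it does not threaten the main comparison. Stratifying by age, gender and operative surgery is sound in principle. The unclear test for stratified times is secondary. The reference to three groups is a wording slip that adds no weight: the plan has "Outcome data of the three groups will be compared", while Sequence Generation describes a lottery "used to assign participants into the two groups".

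**What to change.** Replace the stratification sentence with text to this effect:

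> As exploratory analyses, outcomes will be compared between the gum and honey groups within strata of age, gender and operative surgery, using the t-test for continuous outcomes and the chi-square test for categorical outcomes. Postoperative complications will be compared between the two groups as outcomes only and will not define strata.

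If the report is to claim that the effect differs between strata, test a treatment-by-factor interaction and label it exploratory. Correct the number of groups to two.

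The cost is a wording change to one additional analysis, with no new data and the same software. Treatment comparisons within complication strata are given up. Recovery times by complication status can still be shown descriptively, without a test between arms.

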$$n = \frac{2\sigma^2(z_{1-\alpha} + z_{1-\beta})^2}{(\mu_1 - \mu_2)^2}$$

Where,

n = Sample size = 60

σ = Population standard deviation = 9.2245

σ^2 = Variance = 85.0914

$Z_{1-\alpha}$ = Confidence level 95% = 1.96

$Z_{1-\beta}$ = Power of test = 95%

μ_1 = Population mean Group A = 67.73

μ_2 = Population mean Group B = 75.73

A total sample size of 60 patients (30 patients in each group) is estimated by using 5% level of significance and 95% power of test with expected mean value time to pass flatus in Group A (Chewing Gum) as was 67.73 ± 8.481 hours and Group B (Honey) as 75.73 ± 9.968 hours in the pilot study.

Sampling Technique: Non-probability purposive sampling. Patients admitted to the hospital for stoma reversal procedure will be assigned into Group A or B using a lottery method, ensuring that the sample population is divided into the two groups equally and randomly regardless of their characteristics (33).

Sample Selection:

Inclusion Criteria:

- All patients of age more than 18 years with an Ileostomy
- Undergoing surgery involving reversal of an Ileostomy i.e., Loop Ileostomy, Double Barrel Ileostomy, Ileocolostomy or End Ileostomy
- Time from fashioning of ileostomy to its reversal is of a duration greater than 1 month

Exclusion Criteria:

- Patients with existing complications as mentioned above in the operative definition of postoperative complications
- Patients with malignancy
- Patients with inflammatory bowel disease
- Patients who cannot communicate well
- Patients who have difficulty chewing or swallowing
- Patients who are prohibited from oral intake by the surgeon
- Patients having undergone Ileostomy reversal more than 1 day before being included in the study

Outcome Measures:

- Primary Outcome
 - Time to pass flatus
- Co-primary Outcomes
 - Time to bowel sounds
 - Time to pass feces
- Secondary Outcomes

- Time to full feeds
- Postoperative pain
- Postoperative nausea and vomiting
- Length of postoperative stay /Time to discharge

Data Collection Procedure:

After the approval to carry out this study from the Research Evaluation Unit (REU) College of Physicians and Surgeons Pakistan and the Institutional Review Board (IRB) King Edward Medical University, subjects meeting the operational definitions and the inclusion & exclusion criteria will be enrolled in the study after informed consent.

Randomization:

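### The stratified analysis by age, gender and operation has no test of whether the treatment effect differs between strata and no exploratory label, so chance disagreement between strata could be read as a subgroup effect

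*Combined protocol and SAP*

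**What the plan says.** The Data Analysis Procedure assigns tests by type of variable: "Chi-Square test and logistic regression will be used to analyze the categorical variables whereas continuous variables will be analyzed using student t-test". It sets one significance rule: "p-value of < 0.05 will be considered statistically significant". The next sentence covers subgroups: "Outcome data will be stratified for age, gender, operative surgery, postoperative complications and post stratification chi square test will be applied".

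Nothing else in the document deals with subgroups. There is no treatment-by-factor term, no heterogeneity test, no multiplicity rule and no exploratory label. The plan gives no age cut-point, does not define the levels of the operation factor, and does not list the outcomes to be stratified. Logistic regression is named only for categorical variables in general.

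The trial is sized for the overall comparison: "A total sample size of 60 patients (30 patients in each group) is estimated", from a pilot in which "the mean time to pass flatus in Group A was 67.73 ± 8.481 hours and Group B was 75.73 ± 9.968 hours".

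**The concern.** Stratifying and then applying a two-group test leads to one p-value per stratum. Readers then tend to compare those p-values and conclude that the treatment works in one group only. That inference is not valid. Whether two effects differ is a question about the difference between them, and only an interaction test or an interval for that difference addresses it.

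The risk is high here because a sample sized for one overall comparison is cut into halves or quarters. Each stratum then has moderate or low power, and strata with the same true effect will often fall on opposite sides of 0.05. A uniform benefit could then be reported as confined to one sex, one age band or one type of ileostomy.

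**Working it through.** **Inputs from the document.** Under Sample Size: 30 per arm; difference 75.73 − 67.73 = 8.00 h; SD 9.254 h (pilot table). Under Inclusion Criteria: four ileostomy types. Under Data Analysis Procedure: threshold 0.05.

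**Assumptions, because the document gives no figures.** Factors split evenly and are independent of each other; age has two levels; operation has two or four levels; tests are two-sided. The flatus figures use the t-test that the plan assigns to continuous variables, since chi-square cannot be applied to hours without a cut-point and none is given.

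**1. The plan's own figure.** n = 2σ²(z₁₋α + z₁₋β)²/δ² with one-sided 5% and 95% power: 2 × 9.254² × (1.645 + 1.645)²/8² = 28.97, so 29 per group, as in the pilot table. (The printed z of 1.96 would give 35; that is a separate matter.) With 30 per arm, a two-sided t-test has 91% power overall.

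**2. Power in a stratum.** The noncentrality is δ/(σ√(2/n)).
- 15 per arm (two even strata): 8/(9.254 × √(2/15)) = 2.37 on 28 df, power 63%.
- 7 to 8 per arm (four even strata): power 32 to 36%.

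**3. Disagreement within one two-level factor, same 8 h effect in both strata.** 2p(1 − p) = 2 × 0.628 × 0.372 = 0.467. Simulation with random stratum sizes gives up to about 0.49.

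**4. Across factors (simulation, 60 patients).**

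| Factors | At least one factor disagrees, true 8 h effect everywhere | At least one stratum significant, no effect |
|---|---|---|
| Age, gender | about 65% | about 15–16% |
| Age, gender, operation at 2 levels | about 74% | about 21–22% |
| Age, gender, operation at 4 levels | about 94% | about 29% |

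**5. The test that the sentence names.** For a binary outcome of 50% v 20% (assumed) at 15 per arm, exact chi-square power is 42%. Disagreement is 2 × 0.419 × 0.581 = 0.487, about 49%.

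**6. What an interaction test would do.** With a uniform effect it gives a false finding of a difference in about 5% of trials per factor, and in about 14% for any of three two-level factors. For gender, the standard error of the difference between stratum effects is 9.254 × √(4/15) = 4.78 h. The 95% half-width is 1.96 × 4.78 = 9.4 h, or 9.6 h with t on 56 df. If the stratum effects truly differ by 8 h, power is Φ(8/4.78 − 1.96), about 39%.

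**7. Limits for PONV.** At an assumed 20% rate, four-level operation type by arm gives eight cells of about 7.5 patients, or 1.5 expected events each. The chance that a given cell has no events is 0.8^7.5 = 0.19. The chance of at least one such cell is 1 − (1 − 0.19)^8, about 81%. An ordinary logistic interaction would then usually have no finite estimate.

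**The case against.** The sentence does not say that the arms will be tested separately within each stratum, and the 0.05 rule stands in the preceding sentence. A pooled stratified test of the Mantel-Haenszel type could be meant, and it would not produce the pattern of one stratum significant and another not. This stands as a caution on the wording: the within-stratum reading is the natural one, not a stated fact. It does not remove the point, because a pooled test does not ask whether effects differ either.

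A reader might infer that the trial plans subgroup claims and that these will be mostly noise. The document does not support that. The objective, the hypothesis and the outcome list are all overall comparisons. If there is a true 8 h effect in everyone, a significant stratum is a true positive; the error comes only if someone then concludes that the strata differ.

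A reader might also take 94% as the rate for this plan. It is the top of a range. It depends on treating operation as four strata, and nothing says that the four ileostomy types are the levels to be used. The flatus figures also rest on t-tests, whereas the sentence names chi-square. The binary calculation uses the named test and gives a similar rate per factor, but at assumed event rates.

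Finally, interaction tests have low power at this size. That is true, and it is why the results should be shown as estimates with intervals and called exploratory.

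**Conclusion.** The point holds in this form: the plan prescribes a stratified analysis, most naturally separate tests in each stratum, without any test of heterogeneity and without an exploratory label. Under a uniform 8 h effect and even splits, a two-level factor shows disagreeing strata in about 47 to 49% of trials. At least one factor does so in about 65 to 94%, depending on which factors are used and how operation is divided. With no effect at all, at least one stratum is significant in about 15 to 29%. These rates are for one outcome and rest on the assumed splits.

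The change should be made, but the consequence is limited to how subgroup results are read. The overall comparison of gum and honey is untouched.

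**What to change.** Replace the stratification sentence with wording such as:

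> Consistency of the treatment effect across the baseline factors age, gender and operation type is examined by a treatment-by-factor interaction term in a linear model for each outcome measured in hours. Stratum differences are shown with 95% confidence intervals and no within-stratum p-values. All of these results are exploratory.

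Add the following:
- The age cut-point and the levels of operation type, fixed in advance.
- For PONV, stratum counts and risk differences with exact or score intervals. Fit an interaction only for two-level factors with adequate events, or by a penalised or exact logistic method, and not for four-level operation type.
- A statement that the gender interaction has a 95% half-width of about 9.4 to 9.6 h, so that only large interactions can be detected.
- A statement that postoperative complications are dropped as a stratifier. They arise after randomisation, which is a separate problem that an interaction test would not cure.

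The cost is SAP wording, with no extra data or patients. The linear models are routine; a penalised or exact logistic fit, if chosen, should first be checked for availability in the planned software. The small downside is fewer stratum p-values to report.

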documented every 8 hours in the case report form by the doctor on duty in the ward. As the data collection schedule will be 8 hourly, the doctor on duty in the ward for each day will be responsible for data collection. The doctors on duty in the ward will be trained by the principal investigator about the data collection procedure. The bowel sounds will be auscultated using a stethoscope placed on the right iliac fossa of the patient's abdomen. The patients will be questioned about whether they have passed flatus and feces and at what time they did so. The patients will be questioned about their last time taking full feeds, nausea, vomiting episodes. A visual analog scale for pain will be used to assess the pain score from 0 to 10 i.e. from no pain to the worst possible pain, subjective to each patient. The postoperative antibiotic, IV fluid, analgesic and PPI regimen will be standardized across the study participants. Relevant investigations to confirm the presence of complications will be carried out. All this information will be recorded in the case report form (attached).

Blinding: Selection bias will be addressed by randomly assigning the participants to the groups. Performance bias could not be eliminated due to different surgeons performing the ileostomy reversal surgery. Detection bias will be addressed by keeping the participants unaware of what group they are assigned to and because of the objective nature of the outcome variables. There will still be some detection bias in some respects involving the subjective opinion of the participants e.g. pain score. Intention-to-treat analysis will be done to address attrition bias.

Follow-up: The primary and secondary outcomes will be assessed at 8 hourly intervals after starting either oral chewing gum or honey 24 hours postoperatively and the data will be written manually in the case report form. The final assessment point will be till the time of discharge or a maximum of 5 days/144 hours postoperatively. Data collection will be concluded when the patients will be discharged by the consultant orders in the ward round. Oral chewing gum or honey intake will be stopped on discharge and the patients will be recommended to continue taking oral meals at home. Further follow-up will be not done after the patients are discharged from the hospital.

Data Analysis Procedure:

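### The planned pre- to post-operative change has no pre-operative value in the written schedule, and VAS pain is compared without a baseline, a fixed condition or a time point

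*Combined protocol and SAP*

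**What the plan says.** The Data Analysis Procedure includes, among its descriptive statements, "Any changes in the pre-operative and post-operative values will be calculated in absolute as well as percentages". It names no variable. The same section assigns continuous variables to a Student t-test and mentions no baseline covariate. Pain does not appear in its list of quantitative variables.

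The Follow-up paragraph sets the timing: "The primary and secondary outcomes will be assessed at 8 hourly intervals after starting either oral chewing gum or honey 24 hours postoperatively". The end of assessment is given as "The final assessment point will be till the time of discharge or a maximum of 5 days/144 hours postoperatively". The Implementation paragraph places the start of sips, gum and honey at the same moment: "After a period of 24 hours from the ileostomy reversal surgery, the patients will be asked to start early water sips intake".

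The Operational Definitions count flatus as the time "between the completion of surgery and the documented passage of the first objectively confirmed flatus", feces as the time "between the completion of surgery and the documented first independent bowel movement", and stay as the time "from completion of reversal surgery to the time of discharge from the hospital". Pain is a 0 to 10 VAS of the "subjective pain intensity experienced by the patient at rest or during movement". Outcome Measures lists it as a secondary outcome.

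**The concern.** A change from before to after surgery needs a value before surgery, and the described procedures do not collect one. The sentence therefore commits the analyst to a quantity that cannot be produced from the schedule as written. If a pre-operative VAS did exist, a percentage change would still be undefined for any patient who started at 0, which the scale allows.

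Pain is the outcome for which an early reading would be useful, and three things are left open: whether there is a reading before the first gum or honey, whether the patient is at rest or moving, and which of the repeated scores is tested. At stake are the precision of the pain comparison and the freedom to choose among scores after the data are seen. The primary and co-primary outcomes are not affected.

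**Working it through.** **Step 1. Which outcomes could have a pre-operative value?**

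- Bowel sounds, flatus, feces, full feeds and length of stay: all are hours counted from surgery or its completion. None can have one.
- Nausea and vomiting, and ileus: both are defined as postoperative events. Neither has one.
- Pain: a VAS can be repeated at any time, so a pre-operative or pre-intervention reading is possible. None is described.

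**Step 2. What does the schedule provide for pain?** Gum or honey starts at 24 h and readings follow 8-hourly. If the first comes one interval after the start, it falls at 24 + 8 = 32 h. This is an inference, because no clock time is given. The stated maximum reads both as 5 days (120 h) and as 144 h. That allows up to (120 − 32)/8 + 1 = 12 or (144 − 32)/8 + 1 = 15 scores per patient. No rule says which of them enters the t-test.

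**Step 3. Sample size input.** The plan gives no figure for pain, so the only input taken from it is 30 per arm. That number comes from time to flatus and reproduces with the one-sided formula: 2 × 85.0914 × (1.645 + 1.645)² / 8² = 28.8, so 29 per arm, rounded up to 30 (60 in total). The printed z of 1.96 would give 35 per arm. That is a separate matter, and nothing below depends on it.

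**Step 4. What would a baseline be worth?** All figures are in SD units, with 30 per arm, two-sided 5%, equal SDs at both times, and a correlation r between the baseline and the later VAS. The documents give no r, so 0.3 to 0.7 is an assumption.

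- Later score only: detectable difference at 80% power = (1.960 + 0.842) × √(2/30) = 0.72.
- ANCOVA: multiply by √(1 − r²).
- Change score: multiply by √(2(1 − r)).

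| r | Residual variance removed by ANCOVA | Detectable, ANCOVA | Detectable, change score | Power for 0.5 SD: later score only / ANCOVA / change |
|---|---|---|---|---|
| 0.3 | 9% | 0.69 | 0.86 | 49% / 53% / 37% |
| 0.5 | 25% | 0.63 | 0.72 | 49% / 61% / 49% |
| 0.7 | 49% | 0.52 | 0.56 | 49% / 77% / 71% |

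The 0.5 SD difference is also an assumption. ANCOVA does better than the later score alone at every r shown. A change score does worse than the later score alone when r is below 0.5. A pre-operative VAS would reflect the patient's state before the operation, so its correlation with later surgical pain may be weak. That favours a reading at 24 h.

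**The case against.** **The sentence is generic.** It sits among descriptive statements, names no outcome and no test, and is not tied to pain. This stands. A reader might infer that pain was planned as a change score and then lost that analysis, but the text does not say so. Deleting the sentence removes no stated comparison between arms.

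**A baseline may exist on the form.** The case report form is described as attached and is not in the text supplied. A pre-operative pain field there cannot be ruled out, and a reading close to 24 h is not excluded either. This limits the finding to the written schedule. Such a field would not help the time outcomes, and it would not by itself fix the condition or the time point.

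**There is no bias.** A reader might infer that pain differences already present at 24 h would be credited to gum or honey, particularly as different surgeons operate. The documents do not support that. Allocation is randomised 1:1, nothing links surgeon to arm, and the t-test's standard error already allows for chance imbalance. An imbalance in 24 h pain has a standard error of √(2/30) = 0.26 SD, so one above 0.25 SD in either direction occurs in about one trial in three. Adjustment would recover that as precision. It would not correct a systematic error.

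**The duty doctors are trained and the patient marks the line.** This stands. The change of doctor from day to day is weak evidence of inconsistency. The definition's own allowance for rest or movement is what leaves the measured quantity open.

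**Pain is not the only candidate for a baseline.** Nausea status could also be noted before the first dose. That is true, but pain is the only outcome on a scored scale.

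**Adjustment is optional.** A randomised comparison is valid without it, and at r = 0.3 the gain is only from 0.72 to 0.69 SD. The case for adjusting is that it costs very little.

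**Conclusion.** The concern holds in limited form. As written, the pre- to post-operative change has no inputs for any outcome, subject to the unseen case report form. VAS pain is left to an unadjusted t-test with neither the condition nor the time point fixed. The comparison remains unbiased in expectation, and the loss is precision and consistency of measurement.

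The size of the precision loss rests wholly on the assumed correlation. For r between 0.3 and 0.7, a pre-intervention VAS used as a covariate would be worth as much as having about 33 to 59 patients per arm without one (30/0.91 to 30/0.51). The documents give no pain SD, pilot pain result or target difference, so no effect on a trial conclusion can be shown. Severity is minor, because pain is one of four secondary outcomes.

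**What to change.** 1. Delete the sentence on pre- to post-operative change.
2. At the 24 h contact, immediately before the first gum or honey, record one VAS at rest.
3. Take every later VAS under the same condition. If movement pain is wanted, record it separately.
4. Name one main pain time point on the 8-hourly grid, for example 48 h (24 + 3 × 8), with 72 h (24 + 6 × 8) as supportive. Fixing the order in advance avoids two pain tests of equal standing.
5. Compare arms at the main time point by ANCOVA, adjusted for the 24 h value, and name pain explicitly in the Data Analysis Procedure.

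Pilot mean times to full feeds were 79.47 and 93.33 h. If discharge seldom precedes full feeds (an assumption), few patients would lack a 48 h score.

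The cost is one extra VAS mark at a contact that already takes place, one line on the case report form, and some analysis wording. The downside is that movement pain is not part of the main pain comparison.
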